### Keywords

Autosomal Dominant Polycystic Kidney Disease, Cardiovascular Diseases, Humans, Dietary Inorganic Nitrate, Beetroot Juice, Vasodilation, Nitrate-depleted beetroot juice, Endothelial Dysfunction, Blood pressure, Inflammatory Mediators

## 1. INTRODUCTION

### 1.1 Background and Rationale

#### 1.1.1 ADPKD and the clinical problem

Autosomal dominant polycystic kidney disease (ADPKD) is the most common genetic kidney disease, with a population prevalence of ~1:1000.[2] World-wide it is the most common genetic cause of chronic kidney disease (CKD) and kidney failure in adults.[3] It is caused by loss-of-function pathogenic variants predominantly in *PKD1* (~85% of genetically resolved cases) or *PKD2* (~15% of genetically resolved cases), which encode the polycystin-1 (PC-1) and -2 (PC-2) proteins respectively. *In vivo*, PC-1/2 exists as a membrane complex which has a critical role in modulating extracellular signals to internal molecular pathways that govern cellular differentiation, the cell cycle [4] and the endogenous production of nitric oxide (NO) *via* activation of NO synthase (NOS).[5-7] Loss of PC-1/2 function leads to the progressive formation and growth of multiple fluid-filled kidney cysts, kidney failure and hypertension, which reduces quality of life and causes premature death.[4] ADPKD is a significant burden to the healthcare system due to the cost of kidney replacement therapy (A\$160M per year in Australia alone) [8] and chronic disease complications.

Hypertension develops in 60% of patients with ADPKD by 35 years of age and occurs prior to any reduction in kidney function [8]. It is a major independent risk factor for kidney function decline and cardiovascular complications. [9] Since the availability of dialysis and kidney transplantation, cardiovascular disease is the leading cause of death in ADPKD [10]. Uncontrolled hypertension is associated with increased proteinuria, haematuria, and rate of growth of total kidney volume, as well as decreased renal blood flow [8]. Morbidity and mortality in ADPKD is also associated with increased vascular aneurysm formation and left ventricular hypertrophy, which are driven by hypertension.[11]

In the absence of curative therapies, current medical management is aimed at slowing the rate of kidney cyst growth through lifestyle modification (limiting dietary solute intake and avoiding volume depletion which stimulates AVP release; limiting caloric intake), reducing blood pressure with angiotensin inhibitors and the selective use of tolvaptan in individuals at high-risk of kidney failure. [10]

#### 1.1.2 Potential Role of Reduced NO in the Pathogenesis of ADPKD

The pathogenesis of hypertension in ADPKD is, in part due to, increased intra-renal angiotensin II production in cystic epithelial cells, as well as local renal ischemia due to compression of intra-renal micro-vessels by expanding renal cysts. Hence, angiotensin-converting enzyme inhibitors or angiotensin II receptor blockers are preferred first-line agents in hypertensive ADPKD patients.[8] In addition, the deficiency in endogenous NO synthesis is a central molecular signature of ADPKD and may also be key driver of hypertension and vascular aneurysm formation [12]. Preclinical and observational cohort studies suggest that the reduction in endothelial NO biosynthesis in ADPKD is due to the loss of PC-1/2-mediated activity of NOS [13]. In addition, serum asymmetric dimethylarginine (ADMA), a competitive inhibitor of NOS and an independent predictor of cardiovascular events, is elevated in ADPKD (likely due to reactive oxidative stress)[14] and may also be involved in relative deficiency of NO in ADPKD.[15] The endothelial NO deficiency in ADPKD leads

to endothelial dysfunction, vascular resistance, oxidative stress and inflammation resulting in hypertension and in the long-term, contributing to kidney injury, cardiac dysfunction and aneurysm formation (Figure 1).

#### 1.1.3 Entero-salivary Pathway for increasing Endogenous NO generation in ADPKD

The entero-salivary pathway is a recently described mechanism by which dietary nitrate is converted to nitrite by commensal anaerobic bacteria on the dorsal surface of the tongue.[16] The ingested nitrite is absorbed into the circulation through the stomach where enzymatic and non-enzymatic systems reduce nitrite to NO.[17] Thus, through the entero-salivary nitrate-nitrite-nitric oxide pathway, the dietary intake of inorganic dietary nitrate may restore the endogenous NO deficit in ADPKD, reduce blood pressure and improve endothelial dysfunction.[16] Recently, we found that intracellular levels of NO are reduced by over 75% in human ADPKD cells.[18] However, long-term supplementation of drinking water with oral sodium nitrate intake did not alter the progression of cystic kidney disease in mice with ADPKD, but efficacy on blood pressure reduction was unable to be established due to lack of cardiovascular phenotype in this model. [18]

[figure not shown]
#### 1.1.4 Beetroot Juice (BRJ) as a Dietary Source of Nitrate and potential effects in ADPKD

Nitrates are commonly found in high concentrations in vegetables such as beetroot (*beta vulgaris*), rocket, lettuce, and spinach (~250mg/100g). BRJ has been used as a source of oral nitrate in several studies.[19] In addition to its high nitrate content, BRJ contains other vasoactive components such as vitamin C, magnesium, polyphenols, betaine, and flavonoids that can contribute to improved antihypertensive effects. Vitamin C and polyphenols also participate in non-enzymatic systems of reduction of nitrate to NO.[19] Findings from numerous studies support the efficacy of BRJ in lowering blood pressure; Kapil *et al* showed a reduction of 7.7mmHg in systolic blood pressure (sBP) and 2.4mmHg in diastolic blood pressure (dBP) in drug-naïve and treated hypertensive patients given nitrate-rich BRJ,[20] Kemmner *et al.* showed a 8.2mmHg reduction in sBP in patients with stage 3 CKD.[21] In addition, in a meta-analysis of multiple studies have shown a reduction in sBP including in healthy volunteers with an average reduction in sBP of 4.41-4.4mmHg.[22-27] Previous studies in other populations suggest that a reduction in ~5mmHg is associated with significant reduction in stroke mortality, and with usual targets of achieving a 10-15mmHg reduction in sBP with drug monotherapy or strict adherence to the DASH diet (dietary approach to stop the hypertension diet).[26, 28] In other studies, BRJ increased plasma nitrate levels and improved blood pressure within 4 hours after the consumption of 300mg of nitrate in patients with chronic kidney disease (average eGFR 41 ml/min/m^2). Additionally, dietary nitrate load reduced renal resistive index, a marker for cardiovascular mortality and progression of renal disease, in patients with CKD.[21] Moreover, consumption of nitrate-rich BRJ protected against ischaemia-induced endothelial dysfunction and attenuated platelet aggregation in short-term studies.[29, 30] Preliminary studies in *Pkd1RC/RC* mice showed that betaine (a component of beetroot) reduced renal cyst growth [31, 32].

#### 1.1.5 Safety of BRJ as medium-term intervention in chronic diseases

BRJ is made up of naturally occurring substances, and has been well-tolerated in previous clinical studies with only minimal side effects such as betacyanin pigmented urine (beeturia) and faeces.[19, 20, 26, 33] While there is a theoretical risk of increased production of *N-nitroso* compounds (one of the potential downstream metabolites of nitrate) which has been linked with the development of gastric cancer, these compounds are linked with the consumption of dietary nitrate from red meat and cured meats, rather than nitrate in vegetables, and as a result are hypothesized to be metabolised differently from nitrate-rich vegetables (likely due to the presence of heme-protein).[34, 35] Large case-control population studies have shown that a nitrate-rich vegetable diet is protective against gastric cancer, however a nitrate-rich red meat and cured meat based diet was correlated with a higher risk of gastric cancer.[20, 34-36] Furthermore, a recent large US National Toxicology Program reported a two year long study in which rats who were fed high nitrate in drinking water did not have an increased risk of cancer.[37] Subsequently, large international health surveillance bodies (such as European Commission Scientific Committee for Food and World Health Organisation) have assuaged concerns regarding the cancer risk from nitrate consumption from vegetables, such as beetroot.[34, 35] As a result, the Australian Food Standards Report into nitrate consumption in Australia does not recommend restriction of dietary nitrates from vegetables, especially given the clear health benefit of increased consumption of vegetables in daily diet.[38] Therefore, while the significance of these *N-nitroso* compounds in the a high vegetable nitrate diet are unclear, this study will measure them as part of our exploratory objectives to determine if consumption of BRJ increases the excretion of these compounds.

#### 1.1.6 Study Hypothesis

**Figure 1:** Potential role of exogenous oral nitrates in restoring NO deficit in ADPKD

## 2 RESEARCH PLAN AND TRIAL DESIGN

This is a double-blind (participant/investigator) randomised controlled clinical trial to determine the efficacy, safety, and feasibility of BRJ on lowering blood pressure in participants with treated hypertension in ADPKD.

## 2.1 Objectives

### 2.1.1 Primary Objective:

Determine the efficacy of daily consumption of BRJ (400 mg nitrate) on decreasing clinic systolic and diastolic blood pressure in hypertensive participants with ADPKD over 28 days.

### 2.1.2. Secondary Objectives:

- a) Determine the effect of BRJ on decreasing home systolic and diastolic blood pressure readings
- b) Determine the effect of BRJ on reducing urinary albumin to creatinine ratio
- c) Determine the effect of BRJ on NO metabolites (plasma/urine), and ADMA (plasma) levels;

### 2.1.3. Exploratory Objectives

- (a) Characterisation of the oral microbiome in ADPKD using salivary bacterial genomic data
- (b) Determine the effect of 4 weeks of BRJ consumption on the oral microbiome in ADPKD patients
- (c) Determine if there are any changes in the excretion of *N-nitroso* compounds in urine with BRJ consumption

## 2.2 Endpoints

### 2.2.1 Primary Endpoint

Change in mean automated clinic systolic and diastolic blood pressure before and after treatment with BRJ.

### 2.2.2 Secondary Endpoints

The secondary outcomes assessing treatment efficacy in this study will be the change from baseline in the following:

- (a) mean daily home systolic and diastolic systolic and diastolic blood pressures
- (b) change in urinary albumin to creatinine ratio
- (c) levels of NO metabolites (nitrate and nitrite) in plasma and urine; and
- (d) plasma ADMA levels after dietary nitrate supplementation using BRJ.

To assess safety of chronic nitrate supplementation, the frequency and type of adverse events will be evaluated

To assess adherence to the study procedures, the following will be assessed:

- (a) Number/percent of completed/missed measurement of blood pressure as represented by response to automated text messages or completion of patient diary
- (b) Of measurements captured, number/percent of those who consumed BRJ and took measurements in morning period (6am-9am).

### 2.2.3 Exploratory outcome

To assess the effect of BRJ on the oral microbiome of ADPKD patients, the change from baseline percentage of known nitrous-converting bacteria compared with other oral flora before and after BRJ compared with nitrate-depleted BRJ.

## 2.3 Inclusion and Exclusion Criteria

A total of 60 treated hypertensive participants with ADPKD (as per the inclusion criteria, **Table 1**) will be recruited.

**Table 1.** Participant inclusion and exclusion criteria

| Inclusion Criteria   | Exclusion Criteria   |
|--|--|
| 
 
◆ Diagnosis of ADPKD
 
◆ Age over 18 years old
 
◆ eGFR > 30 mL/min/1.73m^2
 
◆ Receiving at least one anti-hypertensive
 
 | 
 
◆ Inability to provide Informed Consent
 
◆ Labile, unstable uncontrolled hypertension and/or changes in blood pressure treatment in the last 28 days prior to the screening visit that in the opinion of the investigators would confound interpretation of the primary endpoint
 
◆ Non-compliance with daily BP measurements during the screening period
 
◆ Medical conditions or treatments that may interfere with the generation of NO metabolites (such as regular use nitrate drugs, cigarette smoking; unwilling to stop using antiseptic mouthwash; uncontrolled severe hypercholesterolemia)
 
◆ Any serious or other medical conditions that may interfere with follow-up or stability of blood pressure (such as current active malignancies requiring treatment; uncontrolled Diabetes Mellitus (elevated HbA1c > 10%)
 
◆ Dislike of taste of beetroot juice
 
◆ Allergy to beetroot
 
◆ Patients enrolled in other clinical trials
 
◆ Pregnant or Lactating
 
 |

If participants have uncontrolled hypertension they will be advised to consult with their general practitioner and nephrologist for appropriate management. If drug management is required, participants must have stable

blood pressure control treated for at least 28 days before screening can be repeated. The exclusion criteria are based on comorbidities that could potentially confound study endpoints. [39-41] In particular, participants with severe uncontrolled diabetes ( $\text{HbA1c} > 10\%$ ) were excluded based on previous studies that showed lack of effect of BRJ in these participants due to major biochemical perturbations and resulting diminished vascular responsiveness and endothelial damage.[33] However, studies with participants with well-controlled diabetes or early and pre-diabetes were responsive to beetroot juice supplementation and had decreased blood pressure and improved endothelial function after its use, which informed the current study's inclusion of participants with diabetes and controlled  $\text{HbA1c}\%.$ [1, 42] Participants with severe uncontrolled hypercholesterolemia and current cigarette smoking were excluded as they sustain direct endothelial injury and suppression of nitrate metabolism pathways which directly interferes with beetroot juice supplementation.[43, 44]

## 2.4 Study Design

[figure not shown]
The total duration of the study is 35 days. Patients will be screened at Visit 1 and eligible patients will be provided with a blood pressure monitor (oscillometric BP device: UA-651, A&D Medical, Tokyo, Japan) to commence baseline home blood pressure monitoring for a 7 day run-in. Their compliance to daily blood pressure readings will be assessed via automated text message each morning (to which participants will reply with their readings), or with a phone call by study staff on Day 2 and 5 if they opt-out of text messages, and at Visit 2. Replying via text message will be encouraged as the preferred option as it will allow for real-time monitoring and data recording and allow patients to easily contact the study team if they have any issues. Participants will be randomly allocated nitrate-rich BRJ (400mg nitrate) or nitrate depleted BRJ (placebo) in a sealed bag and asked not to open it until instructed to do so after Visit 2.

At Visit 2 (conducted via phone), participants' home blood pressure records will be reviewed for compliance. Participants who have recorded  $<80\%$  of the daily blood pressure readings will be deemed non-compliant and excluded from the trial. Additional exclusion criteria assessed at Visit 2 includes eGFR, fasting lipid and glucose levels, use of antiseptic mouthwash (from V1 to V2 and willingness to comply for remainder of study). Any excluded participants will be asked to return all study equipment and the sealed bag of BRJ. Participants who meet all criteria will be asked to commence the intervention that they were allocated the following morning.

The intervention is BRJ commercially packaged BRJ in 70ml bottles. Participants will be instructed to drink one bottle per day (70ml) and measure their blood pressure at the same time every day. Participants will be asked to send their blood pressures via text or record it in their diary. A daily reminder text message will be sent, unless participants opt-out of this option.

After 28 days, participants will return for Visit 3 for post-treatment assessment and sample collection.

Blood and urine samples will be collected at Visit 1 and 3 for measurement of NO metabolites, ADMA levels and urinary albumin to creatinine ratio. A saliva sample will be collected at Visit 1 and 3 for future genomic analysis of oral bacteria.

**Figure 2.** Study design and participant timeline

The study will be carried out in accordance with the Declaration of Helsinki and is approved by the Western Sydney Local Health District (WSLHD) Human Research Ethics Committee (HREC). Due to the impact of COVID-19, study visits will be performed in the Westmead Institute of Medical Research (WIMR) and at the Department of Renal Medicine, Westmead Hospital to allow flexibility on where participants can be seen based on local public health policy. Participants will be recruited from nephrologists in the Western Renal Service (Westmead, Auburn, Blacktown, Nepean Hospitals) providing a catchment area of 1.2 million people and 400 potential participants with ADPKD.

## 2.5 Recruitment

### 2.5.1 Recruitment targets

A total of 60 participants with ADPKD (as per the inclusion criteria, **Table 1**) will be randomised.

### 6.5.2 Recruitment methods

Participants will be recruited from the Western Renal Service. Multiple strategies will be used to facilitate recruitment. Potential participants will be identified from the Principal Investigator's patient database and databases of previous clinical trial participants who have opted-in to be contacted in future. Potential

participants will further be identified from Western Renal Service nephrologists, either through direct referral to the study team or review of clinic letters and, if available, local databases. Participants will also be recruited passively through flyers (Appendix D) in renal clinics in WSLHD or by internet advertising from the PKD Foundation of Australia via their website and newsletter. Where possible, identified and interested participants will have discussed with their treating nephrologist their suitability for the study and then pre-screened by the study team, by telephone call to determine their eligibility. This process will improve the efficacy of the screening period and reduce participant burden.

To ensure equitable access to the trial from regional areas, a standard travel compensation of \$30 will be provided for each study visit for participants from regional NSW. “Regional NSW” is defined by the NSW government as all areas of the state except the metropolitan areas of Greater Sydney, Newcastle and Wollongong. A map delineating these areas can be found on <https://www.nsw.gov.au/regional-nsw-today>. This compensation is not offered to participants from Greater Sydney as they do not incur the same travel costs.

#### **6.5.3 Informed Consent**

Each investigator has both ethical and legal responsibility to ensure that participants being considered for inclusion in this trial are given a full explanation of the protocol. This shall be documented on a written Master PICF, approved by the WSLHD HREC. Written informed consent will be obtained from all participants. Investigators may discuss the availability of the trial and the possibility for entry with a potential participant without first obtaining consent. However, informed consent must be obtained and documented prior to initiation and completion of any trial procedures.

Specifically, participants will be informed of the expected side effects of beeturia and beet-coloured faeces.(17) As this is a dietary intervention, participants will also be informed of the potential for gastrointestinal side effects and asked to report any symptoms to the trial team immediately. At the time of initial consent, participants will be informed of expectations regarding sharing or re-use of participant data for the means of future research relating to ADPKD. They will be giving the potential to provide extended consent for future use of their data in similar projects relating to ADPKD.

Once the appropriate essential information has been provided to the participant and fully explained in layman’s language by the investigator and it is felt that the participant understands the implications of participating, the HREC-approved written PICF shall be personally signed and dated by both the participant and the person obtaining the consent (investigator), and by any other parties required by the HREC. The participant shall be given a copy of the signed PICF and the original shall be kept on file by the investigator.

#### **6.5.4. Trial registration**

The trial has been registered on [clinicaltrials.gov](https://clinicaltrials.gov) (National Library of Medicine) with registration no. NCT05401409.

## 2.6 Statistical Methods

### 2.6.1 Determination of Sample size

In a previous study of daily BRJ (400mg nitrate) supplementation in hypertensive patients (n=68) for 4 weeks, systolic BP was significantly reduced by 7.7mmHg (3.6-11.8 mmHg,  $p<0.001$ ) at the end of the intervention. The average BP of the two groups were 148 mmHg and 149 mmHg, with standard deviations of the two populations being 10 and 11.[1] We expected to have a similar hypertensive population and to detect this difference in systolic BP with an  $\alpha=0.05$  and power of 0.80, 28 participants are required in the each treatment group. To account for drop-out, the sample size was increased to 30 participants per treatment group (total n=60).

### 2.6.2 Statistical and Analytical Plans

#### *Primary Endpoint Analysis*

The co-primary endpoints are the change in mean of second and third systolic and diastolic BP measurements taken at Visit 1 (pre-intervention) and at Visit 3 (at the end of week 4 of the intervention). Initially, sample mean and standard deviation will be reported at baseline and follow up. Moreover, their mean difference and standard deviation will be reported. Secondly, the main analysis will be conducted using a Gaussian linear mixed effects (LME) model with a first-order autoregressive correlation structure (AR(1)). The repeated measures are the BP results at Visit 1 and Visit 3. An interaction parameter between Visit and Arm of study will be the determinant of a significant difference in BP change between the two arms. The model will be adjusted for the following prognostic factors: age, eGFR and baseline serum nitrate/nitrite levels. The sensitivity analysis will only be adjusted for age and eGFR. Should any variables differ significantly between the two arms, they too will be adjusted for to eliminate the possibility of a confounding effect. No subgroup analyses will be undertaken. All data analysis will be completed in R version 3.6.2 (R Core Team). All (potential) confounding variables will be summarised using t-tests or rank sum tests for continuous variables and chi-squared tests or Fisher's exact tests for categorical variables. Means (standard deviations) and counts (column percentages) as well as relevant p-values will be reported. Hypotheses will be conducted with a two-sided alternative and p-values less than 0.05 will be considered statistically significant.

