| Samples size and statistical analysis | 
In a previous study of daily BRJ (400mg nitrate) supplementation in hypertensive patients (n=68) for 4 weeks, systolic BP was significantly reduced by 7.7mmHg (3.6-11.8 mmHg, <math>p<0.001</math>) at the end of the intervention. The average BP of the two groups were 148 mmHg and 149 mmHg, with standard deviations of the two populations being 10 and 11.[1] We expected to have a similar hypertensive population and to detect this difference in systolic BP with an <math>\alpha=0.05</math>, and power of 0.80 requires a sample size of n=28 in each treatment group, and to account for drop-out, the group size was therefore increased to 30 (total n=60).
 
The pre-specified research aim was to determine whether once-daily administration of dietary nitrate lowered blood pressure in participants with ADPKD. The pre-specified co-primary endpoints are the change in mean of second and third systolic and diastolic BP measurements taken at Visit 1 (pre-intervention) and at Visit 3 (at the end of week 4 of the intervention). Initially, sample mean and standard deviation will be reported at baseline and follow up. Moreover, their mean difference and standard deviation will be reported. Secondly, the main analysis will be conducted using a Gaussian linear mixed effects (LME) model with a first-order autoregressive correlation structure (AR(1)). The repeated measures are the BP results at Visit 1 and Visit 3. An interaction parameter between Visit and Arm of study will be the determinant of a significant difference in BP change between the two arms. The model will be adjusted for the following prognostic factors: age, eGFR and baseline serum nitrate/nitrite levels. The sensitivity analysis will only be adjusted for age and eGFR. Should any variables differ significantly between the two arms, they too will be adjusted for to eliminate the possibility of a confounding effect. No subgroup analyses will be undertaken. All data analysis will be completed in R version 3.6.2 (R Core Team). All (potential) confounding variables will be summarised using t-tests or rank sum tests for continuous variables and chi-squared tests or Fisher's exact tests for categorical variables. Means (standard deviations) and counts (column percentages) as well as relevant p-values will be reported. Hypotheses will be conducted with a two-sided alternative and p-values less than 0.05 will be considered statistically significant.
 
The secondary endpoint of home BP readings is a set of (at most) 28 daily systolic and diastolic BP measurements averaged from daily home readings. Again, a Gaussian LME model with an AR(1) correlation structure will be utilised. The repeated measures are the BP results at each available home reading. An interaction parameter between Day and Arm of study will be the determinant of a significant difference in the BP change between the two arms. The model will be adjusted for the prognostic variables of age, eGFR and baseline nitrate/nitrite levels as described above. The
 |

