#### *Secondary Endpoint Analysis*

The secondary endpoint of home BP readings is a set of (at most) 28 daily systolic and diastolic BP measurements averaged from daily home readings. Again, a Gaussian LME model with an AR(1) correlation structure will be utilised. The repeated measures are the BP results at each available home reading. An interaction parameter between Day and Arm of study will be the determinant of a significant difference in the BP change between the two arms. The model will be adjusted for the prognostic variables of age, eGFR and

baseline nitrate/nitrite levels as described above. The secondary endpoints of change in NO metabolites, serum ADMA and albumin to creatinine ratio will have their differences summarised with sample means, standard deviations, sample mean differences, and sample standard deviations of differences. They too will undergo assessment with a Gaussian LME model as above.

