### *Missing values*

Missing values will not be imputed. An advantage of LME models is that they can automatically tolerate missing values by adjusting the respective covariance estimates. Moreover, missing data for the primary outcome is expected to be minimal as this BP data will be collected at the study visits by the investigators.

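### The planned Visit-by-Arm model cancels its own covariates, so the adjustment and the sensitivity analysis do almost nothing, and Visit 1 BP is not conditioned on

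*Combined protocol and SAP*

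**What the plan says.** Section 2.6.2 (Primary Endpoint Analysis), repeated in the Summary, specifies a Gaussian linear mixed model with AR(1) correlation for each co-primary BP endpoint.

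- Response: "The repeated measures are the BP results at Visit 1 and Visit 3".
- Treatment effect: "An interaction parameter between Visit and Arm of study will be the determinant of a significant difference in BP change between the two arms".
- Covariates: "The model will be adjusted for the following prognostic factors: age, eGFR and baseline serum nitrate/nitrite levels".
- Sensitivity analysis: "The sensitivity analysis will only be adjusted for age and eGFR".
- Extra covariates: "Should any variables differ significantly between the two arms, they too will be adjusted for to eliminate the possibility of a confounding effect".

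The text states no covariate-by-Visit term, does not list Visit 1 BP as a covariate, and does not say that the arms share a common Visit 1 mean. For the NO metabolites, ADMA and albumin-to-creatinine ratio, the Secondary Endpoint Analysis says: "They too will undergo assessment with a Gaussian LME model as above". On missing data: "Missing values will not be imputed".

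**The concern.** A covariate that is constant within a patient, entered as a main effect, moves the patient's overall BP level. The interaction measures the difference between arms in within-patient change, so the covariate has nothing to act on. Four things follow.

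- The main and sensitivity results agree by construction, and a reader could take that agreement for robustness.
- The rule that adds variables differing between arms cannot remove confounding of the change, which is its stated purpose.
- Precision is given up on a co-primary endpoint in a 60-patient trial, although Visit 1 BP is already collected.
- With no imputation, a participant without a baseline nitrate/nitrite assay leaves the main model but stays in the sensitivity model. Any visible gap between the two would then mainly reflect different patients, not adjustment.

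**Working it through.** **1. The plan's own sample size.** Inputs from section 2.6.1: difference 7.7 mmHg, SDs 10 and 11 (midpoint 10.5), power 0.80, alpha 0.05, which section 2.6.2 makes two-sided. The normal formula n = 2(1.960+0.842)²SD²/7.7² gives 26.5 (27 per arm) at SD 10 and 29.2 (30) at SD 10.5. The t-based versions are 28 and 31. The stated 28 is reproduced with SD 10 and the t distribution. This calculation uses a single-visit SD. The SD of change is SD·√(2(1−r)), which equals the single-visit SD only if r = 0.5.

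**2. Why the covariates cancel.** Read literally, with V=0 at Visit 1 and V=1 at Visit 3, A for arm and X for the covariates:

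Y = β0 + β1V + β2A + β3VA + γX + e

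Subtracting the visits within a patient gives D = β1 + β3A + (difference of the two errors). The γX term is gone. With complete pairs, the estimate of β3 is the raw difference between arms in mean change, whatever X contains. With two visits, AR(1) is a single correlation and does not alter this.

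**3. Numerical check.** The planned model was fitted by REML to simulated data.

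- Complete pairs, 28 per arm: in one data set the interaction was −9.985423 (SE 3.009651) with no covariates, with age and eGFR, and with all three, equal to the plain difference in change. Over 300 data sets the largest discrepancy in the estimate was about 1e-12.
- 4 of 60 Visit 3 values missing (SD 10.5; assumed covariate effects 3, −2, −2 mmHg per SD; 2,000 runs): the gap between main and sensitivity results averaged 0.07 mmHg (95th percentile 0.20) at r=0.5 and 0.05 (0.14) at r=0.66. The SD of the estimate itself was 2.3 to 2.8.
- 4 of 56 missing, in a separate 300-run simulation with different assumed covariate effects: the largest such gap was 0.48 mmHg, and the covariates did not improve precision (SD 2.84 with all three, 2.85 with none).

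**4. Precision given up.** Per-patient variance is 2SD²(1−r) for the change score and SD²(1−r²) for ANCOVA on Visit 1 BP. The ratio is (1+r)/2. Power below is from the noncentral t, 28 per arm, SD 10.5, with 54 and 53 degrees of freedom.

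| r (assumed) | Variance ratio | Change score, 7.7 mmHg | ANCOVA, 7.7 mmHg |
|---|---|---|---|
| 0.3 | 0.65 | 62% | 81% |
| 0.5 | 0.75 | 77% | 87% |
| 0.66 | 0.83 | 90% | 95% |
| 0.8 | 0.90 | 99% | 99% |

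Section 1.1.4 also cites "an average reduction in sBP of 4.41-4.4mmHg" from pooled studies. At 4.4 mmHg the powers are 34% and 43% at r=0.5, and 46% and 54% at r=0.66.

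**5. Which r is plausible.** The documents give none. The interval 3.6–11.8 in section 2.6.1, assuming 34 per arm (n=68 split evenly), implies SE = 8.2/(2×1.9966) = 2.0535 and SD = 2.0535/√(2/34) = 8.47.

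- If the interval is for a difference in change, r = 1 − 8.47²/(2SD²), which is 0.64 at SD 10 and 0.70 at SD 11.
- If it was baseline-adjusted, r = √(1 − 8.47²/SD²), which is 0.53 and 0.64.

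**6. Cost of the extra covariates.** With Visit 1 BP and all three covariates at n=60, simulated variance ratios against the change score, over two sets of runs, were 0.63–0.68, 0.75–0.78, 0.86–0.90 and 0.93–0.95 at r = 0.3, 0.5, 0.66 and 0.8. ANCOVA is better at every r, but by less at high r than (1+r)/2 suggests.

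**The case against.** The strongest reply is that section 2.6.2 is prose, not a model formula. Covariate-by-Visit terms or a common Visit 1 mean may have been intended. Either would change the result: in the example above, covariate-by-Visit terms moved the estimate from −9.99 to −10.36. The plan states neither, and an analyst following it literally would fit the model that cancels. The text also does not say that eGFR is the screening value, and the Summary lists blood for eGFR among the study procedures. An eGFR that varied by visit would not cancel, but it would be a post-randomisation covariate. Both points show that the model has to be written out; neither rescues it as it stands.

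It is also true that the endpoint is change from baseline and the interaction estimates it without bias, so validity is not at issue. Over the implied r of 0.53–0.70 the planned analysis has about 79%–94% power at 7.7 mmHg, against 89%–97% for ANCOVA. The target is therefore roughly met either way, and r=0.3 lies outside that range. At 4.4 mmHg both analyses are underpowered. These points limit the size of the precision loss; they do not touch the uninformative sensitivity analysis, which does not depend on r.

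The missing-assay problem is hypothetical, since blood is drawn from everyone at Visit 1 and no failure rate is given. Even after the fix, the sensitivity analysis differs from the main result by only about a tenth of the estimate's SD, so it remains a modest check.

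**Conclusion.** The concern holds. As specified, the covariate adjustment, the age and eGFR sensitivity analysis and the add-if-different rule have no effect on the primary treatment estimate with complete pairs, and almost none with the few missing values the plan expects. This assumes covariates entered as main effects, Visit and Arm main effects present, and screening eGFR. The estimate is unbiased; what is lost is precision and a meaningful sensitivity analysis. For r between 0.53 and 0.70, conditioning on Visit 1 BP alone would lower the variance by about 15% to 23% (1 − (1+r)/2), less once all three covariates are added at this sample size. Near r=0.8 the gain is negligible. The range for r rests on an even split of the earlier study and SDs of 10 to 11; the simulated gaps rest on assumed covariate effects. The change should be made, but the trial is not invalid without it.

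**What to change.** Before unblinding, write out the primary model. The preferred form is a constrained-baseline longitudinal model: a Visit 1 mean common to both arms, Visit, Visit-by-Arm, and age, eGFR and baseline nitrate/nitrite each with a covariate-by-Visit term. It keeps participants with only one BP value. ANCOVA of Visit 3 BP on Arm, Visit 1 BP and the same three covariates is simpler, but it loses anyone without Visit 3 BP.

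Also:

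- State that eGFR is the screening value.
- Fix the covariate list in advance and delete the rule that adds variables found to differ between arms.
- Keep the age and eGFR sensitivity analysis. It can then differ from the main result (simulated average gap 0.23 mmHg at r=0.66 and 0.29 at r=0.5; 95th percentiles 0.75 and 0.95), and it retains anyone without a baseline nitrate/nitrite assay.
- Use the same form for albumin-to-creatinine ratio, ADMA and NO metabolites. For the nitrate/nitrite endpoints, enter the baseline value once only.

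The cost is one degree of freedom for Visit 1 BP under ANCOVA, or up to three covariate-by-Visit terms, and no new data. The Summary says that study activity began in May 2022, so this needs a dated, justified change to the analysis plan, made before unblinding.
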